Project Title: Optimizing Ankle Exoskeleton Assistance for Walking Across the Life Span

NCT Number: NCT04033146

Date: April 25, 2024

Study Protocol

We used commercially available bilateral ankle exoskeletons (Dephy Inc, Boxborough, MA) with custom controllers to provide plantarflexion assistance to each user. The exoskeletons have on-board encoders and inertial measurement units to enable state-based control.

Participants walked in six conditions: (1) without ankle exoskeletons (NoExo), (2) ankle exoskeletons without assistance (NoTorque, (3) exoskeletons with springlike assistance (Spring), and exoskeletons with three motorized assistance strategies with increasing peak torque: (4) 10 N-m (MotorLow), (5) 20 N-m (MotorMed), (6) 30 N-m (MotorHigh). The spring-like assistance used impedance control without damping to apply torque with a spring stiffness of 70 Nm/rad. The assistance began in the foot-flat position after heel strike and ended at toe off mimicking a spring and clutch mechanism than enabled storage and release of elastic energy in stance and free foot motion during swing. The torque profile for the motor assistance conditions was specified by a spline generated from four nodes: peak time, rise time, fall time, and peak torque. The spline settings were based on a previously published study that used human-in-the loop optimization to minimize metabolic cost for a group of younger adults walking at medium speed. For this experiment, we scaled the HiLO torque pattern to match our desired low, medium and high peaks values at preset values of 10, 20, and 30 N-m.

Participants completed testing over three sessions walking at 1.25 m/s on an instrumented split-belt treadmill (CAREN, Motek, Netherlands). The sessions were conducted in a set order: 1) habituation, 2) gait mechanics, and 3) steady-state metabolic energy consumption. Waiting periods between sessions were minimized to allow for learning and retention of walking patterns with exoskeleton assistance (2-7 days on average).

Session 1 – Habituation.

Previous work has shown the importance of habituation for the acceptance of assistance from exoskeletons. In the first session, each participant walked with spring-like assistance for three, seven-minute intervals for a total of 21 minutes. They also walked with motorized assistance for three, seven-minute intervals while increasing peak torque (10, 20, 30 Nm) with each bout.

Session 2 - Gait Mechanics.

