Project Title: Optimizing Ankle Exoskeleton Assistance for Walking Across the Life Span

NCT Number: NCT04033146

Date: April 25, 2024

Statistical Analysis Plan

The goal of the study is to evaluate the effects of bilateral ankle exoskeleton assistance on both young and older participants' metabolic energy cost during walking.

We seek to test three hypotheses:

H1. Bilateral ankle exoskeletons that provide 'motor-like' assistance will result in lower net metabolic power than those providing 'spring-like' assistance for young adults.

H2. Bilateral ankle exoskeletons that provide 'motor-like' assistance will result in lower net metabolic power than those providing 'spring-like' assistance for older adults.

H3. Bilateral ankle exoskeletons will result in lower net metabolic power for older versus young adults regardless of assistance strategy (i.e., for 'motor-like' or 'spring-like' assistance).

To test these hypotheses we will execute a repeated measures study design.

We will compute means of the primary outcome measure:

Net Metabolic Power (watts/kg)

for 6 bilateral ankle exoskeleton conditions:

- C1. Without ankle exoskeletons (NoExo) across
- C2. Bilateral ankle exoskeletons without assistance (NoTorque)
- C3. Bilateral ankle exoskeletons with spring-like assistance (Spring)
- C4. Bilateral exoskeletons with low-level motor-like assistance (10 Nm) (MotorLow)
- C5. Bilateral exoskeletons with medium-level motor-like assistance (20 Nm) (MotorMed)
- C6. Bilateral exoskeletons with high-level motor-like assistance (30 Nm) (MotorHigh)

for participants in two age categories:

X young adults (18-45 yrs)

Y older adults (>65 yrs).

To address H1 we will perform a two-way ANOVA on the young adult data (factors: participant (random) = X levels; exoskeleton condition = 6 levels) to test for a significant effect of exoskeleton condition on net metabolic power (watts/kg) ($p < \alpha = 0.05$; SPSS 21, IBM, USA). If exoskeleton condition is significant, we will perform post-hoc pairwise comparisons with a Bonferroni correction to test whether net metabolic power (watts/kg) is lower for MotorHigh vs. Spring; MotorMed vs. Spring; and MotorLow vs. Spring.

To address H2 we will repeat the analysis used for H1 on the older adult data.

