To address H3 we will compute mean differences with respect to NoTorque for spring-like (C4-C2) and motor-like (C6-C2; C5-C2; C4-C2) assistance conditions for both young and old adults. Then we will perform four independent t-tests with a Bonferroni

correction to test whether the difference in net metabolic power (watts/kg) is greater for older versus young adults for Spring, MotorLow, MotorMed, and MotorHigh bilateral exoskeleton assistance.

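### The SAP's H3 analysis codes the Spring contrast as MotorLow, and its literal test direction is opposite to H3; correct both, and say whether H3 is claimed jointly or per strategy

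*SAP*

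**What the plan says.** The SAP's list of conditions gives "C3. Bilateral ankle exoskeletons with spring-like assistance (Spring") and assigns C4 to MotorLow, C5 to MotorMed, C6 to MotorHigh and C2 to NoTorque.

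H3 predicts "lower net metabolic power for older versus young adults regardless of assistance strategy", with the gloss "i.e., for 'motor-like' or 'spring-like' assistance".

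The H3 analysis paragraph forms differences from NoTorque for "spring-like (C4-C2) and motor-like (C6-C2; C5-C2; C4-C2) assistance conditions" in both age groups. It then plans the tests: "Then we will perform four independent t-tests with a Bonferroni" correction, asking whether the difference in net metabolic power "is greater for older versus young adults for Spring, MotorLow, MotorMed, and MotorHigh bilateral exoskeleton assistance".

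The SAP states alpha = 0.05 for the H1 ANOVA and does not restate it for H3. It does not give the sidedness of the H3 tests or say how many of the four must succeed. The group sizes are the placeholders X and Y.

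**The concern.** The sentence that defines the H3 contrasts is the one a programmer would implement. Followed to the letter, it yields no Spring contrast, although H3 covers spring-like assistance explicitly.

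The direction has a similar problem. Each contrast is assisted minus NoTorque, so a metabolic saving is a negative number. If older adults save more, their difference is lower than that of the young, while the SAP tests whether it is greater. A one-sided test in that literal direction would look for the opposite of H3. A two-sided test would avoid this, but sidedness is not stated.

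A secondary point is how the four results combine. If, say, two of four tests are significant, H3 could be reported as supported or not supported, depending on whether it is read as one claim about every strategy or as four separate claims. That choice should not be left until the results are known.

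**Working it through.** **1. Contrast codes, SAP list against SAP H3 paragraph.**

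| Strategy | Code in the list | Contrast implied | Contrast written |
|---|---|---|---|
| Spring | C3 | C3-C2 | C4-C2 |
| MotorLow | C4 | C4-C2 | C4-C2 |
| MotorMed | C5 | C5-C2 | C5-C2 |
| MotorHigh | C6 | C6-C2 | C6-C2 |

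Four contrasts are written, but only three are distinct. C4-C2 appears twice and C3-C2 never.

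**2. Direction.** Let D = assisted minus NoTorque, and let Δ = mean D (older) minus mean D (young). If assistance saves older adults 0.25 W/kg more than young adults (an assumed value), Δ = -0.25. H3, in the form that the analysis gives it, is therefore Δ < 0. The literal test is Δ > 0. If D were NoTorque minus assisted, the same facts would give Δ = +0.25, and *greater* would be correct.

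**3. Cost of the literal direction if one-sided.** Assumed: trial SD 0.2 W/kg, shared response SD 0.1, and both D's in question taken against one NoTorque trial.
- SD of D = √(0.2² + 0.2² + 0.1²) = √0.09 = 0.3.
- With 15 per group, the SE of Δ = 0.3 × √(2/15) = 0.1095, so Δ = -0.25 lies 0.25/0.1095 = 2.28 SE below zero.
- The chance that an upper-tailed 0.05 test rejects is about 1 - Φ(1.645 + 2.28) = 1 - Φ(3.93), under 0.1%.

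**4. Multiplicity.** The SAP gives no H3 figure to reproduce. Assume the family alpha is 0.05.
- Per-test level: 0.05/4 = 0.0125.
- Strategy-specific claims: the chance of any false claim is at most 4 × 0.0125 = 0.05. With the codes as written, three distinct tests give at most 3 × 0.0125 = 0.0375.
- Joint claim requiring all four: the worst-case error is that of one test, so 0.0125 with Bonferroni and 0.05 without.

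Error is not inflated on either reading. Under a joint claim the price is power. For tests with 80% power each at two-sided 0.05, the standardised effect is 1.960 + 0.842 = 2.802. At 0.0125 the critical value is 2.498, so per-test power is Φ(2.802 - 2.498) = Φ(0.304) = 61.9%. All-four power then depends on the assumed correlation between tests:

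| Correlation | All four at 0.05 | All four at 0.0125 |
|---|---|---|
| 0 | 41.0% | 14.7% |
| 0.5 | 55.6% | 31.4% |
| 0.9 | 70.2% | 49.1% |

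**5. Literal-execution bound for the coding error.** This is a simulation with the SDs of step 3, a true difference of 0.25 W/kg in the three motor strategies and none in Spring, two-sided tests, and success counted in the H3 direction. The table shows how often every contrast is significant.

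| n per group | As written, 0.05 | Spring as C3-C2, 0.05 | As written, 0.0125 | Spring as C3-C2, 0.0125 |
|---|---|---|---|---|
| 10 | 19% | 1.9% | 6% | 0.3% |
| 15 | 36% | 2.2% | 15% | 0.4% |
| 20 | 52% | 2.4% | 27% | 0.5% |

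These figures need an analyst to run MotorLow twice, label one copy Spring and overlook two identical results. They also need a true Spring effect of zero. They bound what could happen and do not predict it.

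**The case against.** The intent can be recovered from the text. The miscoded contrast is itself labelled spring-like, and the following sentence counts four tests and names Spring among them. A careful analyst would notice duplicate output. Likewise, *greater* can be taken as a greater reduction, which agrees with H3. Both arguments stand as to intent. They do not remove the contradiction between the codes and the list, or supply a sign.

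A reader might go further and infer any of the following. The documents support none of them.

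- *Spring is left out of H3 by design.* The named list of tests includes it.
- *H3 is plainly a joint claim, so the analysis does not match it.* The SAP's own gloss joins the strategies with *or*. On a per-strategy reading, four Bonferroni-corrected tests match the hypothesis.
- *One significant test is enough for H3.* The SAP states no such rule.
- *Bonferroni is the wrong correction.* It is valid for strategy-specific claims and only conservative for a joint one.
- *All four tests at 0.05 is the rule the SAP should have used.* It is one option and a demanding one. With the SDs above, 0.25 W/kg in three strategies and 0.10 in the fourth, it succeeds in 6% / 11% / 15% of trials at n = 10 / 15 / 20. At least one Bonferroni-corrected strategy-specific claim is made in 42% / 61% / 75%.

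The power figures also cannot show a material loss in this study, because the inputs are assumed. With 30 per group and a difference of 0.36 W/kg, all four succeed in 93% at 0.0125 against about 99% at 0.05.

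**Conclusion.** The concern holds for the contrast code and the direction of the test. Both are errors or contradictions in the operative H3 text, and showing them requires no assumption. The code is probably a typing error. The direction is opposite to H3 if read literally, and consistent with it if *greater* means a greater reduction. This takes H3 as the analysis does, as a statement about change from NoTorque.

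The missing statement of what H3 claims is secondary. The wording allows a joint or a per-strategy reading, and the planned correction controls error under both, assuming a family alpha of 0.05. The H3 alpha and sidedness are missing detail. So is the number of comparisons needed for H1 and H2 ("lower for MotorHigh vs. Spring; MotorMed vs. Spring; and MotorLow vs. Spring"), whose wording implies no particular rule.

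The power figures and the coding table are illustrative. They rest on assumed SDs, effects, correlations and group sizes.

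**What to change.** 1. In the H3 analysis paragraph, change the spring-like contrast from C4-C2 to C3-C2.
2. Write the H3 alternative as older minus young in (assisted minus NoTorque) < 0. Alternatively, define the difference as NoTorque minus assisted and keep *greater*.
3. State whether the tests are one- or two-sided, and confirm the H3 family alpha.
4. State whether H3 is claimed per strategy or jointly. For per-strategy claims, keep the four Bonferroni-corrected tests. For a joint claim, either require all four at the Bonferroni level, which is conservative, or require all four at 0.05.
5. Report all four differences with confidence intervals in either case.

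All of this is SAP wording and needs no new data. Timing restricts one option. The Protocol is in the past tense ("Participants completed testing over three sessions walking at 1.25 m/s on an instrumented split-belt treadmill"), the SAP of the same date is in the future tense, and neither says whether H3 results had been seen. Moving from 0.0125 to 0.05 for an all-four rule is acceptable only if they had not; otherwise that rule should be labelled post hoc. The corrections to the code and the sign should be dated and recorded.

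### H3 claims a lower level of net metabolic power in older adults, but its only test compares changes from NoTorque, with one mislabelled contrast and an ambiguous direction

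*SAP*

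**What the plan says.** The SAP's list of hypotheses gives H3 as: "Bilateral ankle exoskeletons will result in lower net metabolic power for older versus young adults regardless of assistance strategy". A closing parenthesis explains the last words as covering the motor-like and the spring-like type of assistance.

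The SAP's closing paragraph holds the only analysis of H3. It will "compute mean differences with respect to NoTorque for spring-like (C4-C2) and motor-like (C6-C2; C5-C2; C4-C2) assistance conditions" in each age group. It continues: "Then we will perform four independent t-tests with a Bonferroni" adjustment. The stated purpose of these tests is to "test whether the difference in net metabolic power (watts/kg) is greater for older versus young adults", and the paragraph names Spring, MotorLow, MotorMed and MotorHigh as the four comparisons.

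The SAP's list of conditions defines the codes: "C3. Bilateral ankle exoskeletons with spring-like assistance (Spring") and "C4. Bilateral exoskeletons with low-level motor-like assistance (10 Nm) (MotorLow"). C2 is NoTorque.

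The SAP's stated goal is to "evaluate the effects of bilateral ankle exoskeleton assistance" on metabolic cost in both age groups. Group sizes appear only as X and Y. No SD, effect size, sidedness or adjusted alpha is given for H3. The 0.05 level is stated for the H1 analysis, which H2 repeats.

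**The concern.** The hypothesis and its test concern different quantities. H3 speaks of a level and names no reference condition. H1 and H2 also speak of lower net metabolic power, and they are tested on net metabolic power itself. H3 alone is tested on a change, and no other analysis in the SAP compares the age groups. A significant result would show that assistance altered cost by a different amount in older adults. A reader of H3 would take it to show that older adults walked at lower metabolic power.

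Three further gaps affect the same result:

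- Followed by code, the row labelled Spring would hold the MotorLow comparison, and Spring would have none.
- The word chosen for direction fits either a larger signed value or a larger reduction, and these are opposites here.
- H3 is asserted across types of assistance, but nothing says which of the four tests must succeed. A single significant condition could be reported as confirming the whole statement.

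**Working it through.** The plan gives no sample size, power or effect figure for H3, so there is none to reproduce.

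**1. Contrast labels (SAP list of conditions against the H3 paragraph).**

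| Comparison named | Printed | By the SAP's definitions |
|---|---|---|
| Spring | C4-C2 | C3-C2 |
| MotorLow | C4-C2 | C4-C2 |
| MotorMed | C5-C2 | C5-C2 |
| MotorHigh | C6-C2 | C6-C2 |

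Four tests are announced, but only three distinct contrasts are printed.

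**2. Level against change.** For any assisted condition, with every gap taken as older minus young:

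level gap = NoTorque gap + change gap.

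Assumed values in W/kg, with young adults going from 3.0 to 2.9 (change -0.1):

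- Older 4.0 to 3.6 (change -0.4): change gap -0.4 + 0.1 = -0.3; level gap (4.0 - 3.0) - 0.3 = +0.7. H3 as worded is false.
- Older 3.2 to 2.8 (change -0.4): change gap -0.3; level gap (3.2 - 3.0) - 0.3 = -0.1. H3 as worded is true.

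The planned test sees -0.3 in both. At that change gap, NoTorque gaps of -0.3, 0, +0.3, +0.5 and +1.0 give level gaps of -0.6, -0.3, 0, +0.2 and +0.7. H3 as worded fails whenever older adults' NoTorque power exceeds young adults' by at least the extra reduction.

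**3. Direction.** On the printed contrasts a benefit is negative. In the example, older minus young is -0.4 - (-0.1) = -0.3, so the larger benefit is the smaller signed number. With reduction defined as C2 - Ck, the same data give 0.4 - 0.1 = +0.3. A two-sided p-value is the same either way. Only a one-sided test in the literal direction would look in the wrong tail.

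**4. Decision rule.** Assumptions: family alpha 0.05 for H3, so Bonferroni gives 0.05/4 = 0.0125 per test; 15 per group; an age difference in reduction of 1.0 SD wherever one exists; equal correlation of 0.3 to 0.8 between the four changes; a test counts only if the older group has the larger reduction. Results are from simulation with 40,000 replicates.

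*Spring has no age difference; each motor condition has 1.0 SD:*

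- At least one of four significant at 0.0125: 69% to 84% of trials. Most of this is correct detection of the motor effects. It becomes an error only if reported as holding for every type of assistance.
- All four significant at 0.0125: under 1%.
- All four significant at two-sided 0.05: about 2% to 2.5%. The ceiling is 0.05/2 = 2.5%, because the null condition must itself succeed in the right direction.

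*All four conditions have 1.0 SD:*

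| Rule for the overall claim | Claimed (correlation 0.3 / 0.5 / 0.8) |
|---|---|
| All four at 0.0125 | 16% / 22% / 34% |
| All four at 0.05 | 41% / 48% / 59% |
| Spring and at least one motor level, at 0.0125 | 48% / 49% / 50% |

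For one condition, noncentral-t power at two-sided 0.0125 is 0.325, 0.535 and 0.703 with 10, 15 and 20 per group. The choice of rule therefore moves the H3 conclusion a good deal under any of these assumptions.

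**The case against.** The strongest reply is that H3 plainly means a larger effect of assistance in older adults. The stated goal concerns effects of assistance, H3 speaks of what exoskeletons bring about, and the analysis paragraph refers everything to NoTorque. That is the natural reading, and it stands as a defence of the planned test, which should be kept. It does not rescue the sentence. H3 as printed still supports a claim about level that the test cannot deliver.

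The code slip is also easily recovered, since the same paragraph names Spring and MotorLow separately. A reader might infer that Spring would go untested, or that a wrong result would be published. The documents do not support that; they show a misprint.

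On direction, a reader might infer a one-sided test in the wrong tail. The SAP does not say that the tests are one-sided, and two-sided testing removes most of the problem.

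On the decision rule, a reader might infer that all four conditions must succeed, each at 0.0125. The SAP does not say so. H3's own parenthesis names two types of assistance, not four conditions, so Spring plus a motor level also fits. An all-must-succeed claim does not need Bonferroni either, as the 2.5% ceiling shows. What stands is that the rule is unstated.

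Finally, the Protocol is in the past tense ("Participants completed testing over three sessions walking at 1.25 m/s") while the SAP is in the future tense. A reader might infer that H3 was framed after the results were known. The documents do not show when data were examined, so this supports only a conditional disclosure.

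**Conclusion.** The point holds as a mismatch between hypothesis and test. The change-from-NoTorque comparison cannot show that older adults have lower net metabolic power, and this follows from an identity that needs no assumed values. The mislabelled Spring contrast is certain from the text but minor. The ambiguous direction is real and largely cured by two-sided testing. The missing rule for the overall claim is real, but the documents do not imply one particular rule.

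The numerical size is illustrative throughout: the baselines, 15 per group, 1.0 SD and the correlations are all assumptions. H3 needs correcting before it is reported, because one of the three hypotheses has no test matching its wording. The planned comparison itself is sound once the hypothesis is restated to fit it.

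**What to change.** In the SAP:

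1. Correct the Spring contrast to C3 and define reduction = C2 - Ck for k = 3, 4, 5, 6, so that a positive value is a benefit.
2. Restate H3 as a larger reduction in net metabolic power relative to NoTorque in older than in young adults.
3. Test older minus young reduction with two-sided t-tests. A condition supports H3 only if its test is significant and the estimate is positive. Keep Bonferroni (0.0125) for condition-specific claims.
4. For the overall claim across types of assistance, state in advance which conditions must succeed: at least Spring and motor-like assistance, following H3's own parenthesis, and all four if the claim covers every motor level. If all four are required, test each at two-sided 0.05 with the right sign and without Bonferroni. If any one motor level may stand for motor-like assistance, keep 0.0125. One significant condition alone must not be reported as confirming H3 overall.
5. Report each age group's mean reduction with a 95% CI, so that less harm is not read as benefit. Do not conclude from these tests that older adults have lower net metabolic power.
6. If data had already been seen, disclose the restatement as made after data collection.

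The cost is wording and labels, with no new data. The H3 claim narrows from level to change. Two-sided testing gives up some power against a correctly directed one-sided test at 0.0125: 54% against 65% per condition at the assumed 15 per group and 1.0 SD. An all-four rule costs more (41% to 59% at 0.05, same assumptions), but condition-specific findings remain reportable.
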